**Adverse Device Effect (ADE):** 

All untoward and unintended responses to the medical device.

The phrase "responses to a medical device" means that a causal relationship between the device under

investigation and an AE is at least a reasonable possibility, i.e., the relationship cannot be ruled out.

All cases judged by either the reporting medically qualified professional or the sponsor as having a

reasonable suspected causal relationship to the device qualifies as a device effect.

Clinical Investigation Plan **CRE 027** Date 14 04 20

Version Number 1.0

CONFIDENTIAL

Page 26 of 42

This also includes any event resulting from insufficiencies or inadequacies in the instruction for use or

deployment of the device and includes any event that is a result of a user error.

**Serious Adverse Event (SAE):** 

'Serious adverse event' means any adverse event that led to any of the following:

death,

• serious deterioration in the health of the subject, that resulted in any of the following:

o life-threatening illness or injury,

o permanent impairment of a body structure or a body function,

o hospitalisation or prolongation of patient hospitalisation,

o medical or surgical intervention to prevent life-threatening illness or injury or

permanent impairment to a body structure or a body function,

o chronic disease,

• foetal distress, foetal death or a congenital physical or mental impairment or birth defect

**Serious Adverse Device Effects (SADE):** 

A serious adverse device effect (SADE) is any untoward medical occurrence seen in a patient that can

be attributed wholly or partly to the device which resulted in any of the characteristics or led to a

characteristics of a Serious adverse event.

SADE is also any event that may have led to these consequences if suitable action had not been taken

or intervention had not been made or if circumstances has been less opportune.

All cases judged by either the reporting medically qualified professional or the sponsor.

**Unanticipated Adverse Device Effect (UADE):** 

Any serious adverse device effect on health or safety or any life-threatening problem or death caused

by, or associated with a device, if that effect, problem, or death was not previously identified in

Clinical Investigation Plan

CONFIDENTIAL

Page 27 of 42

nature, severity or degree of incidence in the investigational plan or application (including a

supplementary plan or application), or any other unanticipated serious problem associated with a

device that related to the rights, safety or welfare of the subject.

Reporting of AE

All AE's occurring during the study observed by the investigator or reported by the participant,

whether or not attributed to the device under investigation will be recorded on the CRF as specified in

the protocol. All ADE's will be recorded in the CRF.

The following information will be recorded: description, date of onset and end date, severity,

assessment of relatedness to device, other suspect drug or device and action taken. Follow-up

information should be provided as necessary.

The relationship of AEs to the device will be assessed by a medically qualified investigator or the

sponsor/manufacturer and will be followed up until resolution or the event is considered stable.

All ADE that result in a participant's withdrawal from the study or are present at the end of the study,

should be followed up until a satisfactory resolution occurs.

Where relevant, any pregnancy occurring during the clinical study and the outcome of the pregnancy,

should be recorded and followed up for congenital abnormality or birth defect.

Reporting Procedures for All SAEs/ SADEs/ UADEs

Considering the data collected in this study is on a CE marked product being used within its intended

use, and the retrospective nature of the study, all SAE/SADE/UADEs reported as part of the study

will be managed in accordance with Xiros Standard Procedure for Product Events Reports and

Vigilance.

Clinical Investigation Plan CRE 027 Date 14 04 20

Date 14\_04\_20 Version Number 1.0 CONFIDENTIAL

Page 28 of 42

**12.** STATISTICS

**Description of Statistical Methods** 

The primary analysis will summarise the re-rupture rate of patients. The number and percentage of

patients who have experienced a re-rupture will be reported. Additionally, a corresponding confidence

interval will be reported for the percentage of patients with a re-rupture. The analysis will be performed

for all patients combined, and also separately for the subgroups of patients receiving JewelACL alone,

and those receiving JewelACL in combination with autograft.

A single analysis will be performed at the end of the study, no interim analyses will be performed.

The Number of Participants

The sample size was calculated to ensure an accurate estimate of the re-rupture rate in patients

receiving JewelACL. Based on previous data and clinical experience, the re-rupture rate is expected to

be 10% (or less). The sample size was calculated so that the uncertainty in the calculated compared to

the 'true' population percentage is not more than  $\pm 6\%$ . Using a 95% level of confidence, it is calculated

that 96 subjects are required for the study. In order to allow for a 20% drop-out, 120 subjects will be

recruited into the study.

The Level of Statistical Significance

As there are no planned hypothesis tests, the level of significance is not relevant to this study. All

confidence intervals will be calculated using a 95% confidence level.

Criteria for the Termination of the Study

Not Applicable. The study will not be terminated based on any data collected.

Procedure for Accounting for Missing, Unused, and Spurious Data

The primary analysis will be performed on the collected data. No data imputations will take place, with

patients with missing data excluded from the analysis. Any spurious data values will be checked against

source material to verify the validity.

Clinical Investigation Plan

CONFIDENTIAL

Page 29 of 42

#### Procedures for Reporting any Deviation(s) from the Original Statistical Plan

Any deviations from the original analysis plan will be documented and justified in the final analysis report.

#### **Inclusion in Analysis**

All patients who meet the entry criteria will be included in the study.

**13.** RISK AND BENEFITS

13.1 Benefits

The information collected in this clinical investigation will be added to the current knowledge

and understanding of treatment options for patients requiring ACL reconstruction. It is

expected that recipient patients of the JewelACL device will have the same benefits as

patients implanted with autografts and other commercially available ACL devices used for

ACL reconstruction. It will also provide long term outcome data to reassure surgeons of the

device's performance.

A minimum of 5 year follow up data on the JewelACL device will be beneficial to surgeons

as it will provide assurance of the device's safety and performance over the long term.

13.2 Risks

With the review of medical records, the primary risk is that of breach of confidentiality of

data. All source data is to be held within the reporting hospital site and no identifiable details

are to be included in any data reports.

13.3 Anticipated Adverse Device Effects

Adverse events potentially associated with the use of the JewelACL device and potential

complications are documented in the Instructions for Use. Instructions for Use are available

upon request.

13.4 Risk Control Measures

Actions to control or mitigate risks at the clinical investigation centre will include the

selection of qualified and experienced investigators. No patient identifying data will be

CONFIDENTIAL

collected for the study.

13.5 Risk to Benefit

Clinical Investigation Plan CRE 027

Page 31 of 42

The risks associated with the use of the JewelACL device are anticipated to be comparable to those associated with the use of other commercially available devices used for ACL reconstruction. Given that the study is retrospective in nature and does not introduce any new clinical risks to the patient, the benefit of this study outweighs any risks to the patient.

14. CLINICAL DATA HANDLING

The Sponsor will be responsible for the handling of study data. All study data will be entered on the

Electronic Case Report Form.

14.1 Direct Access to Source Data/Documents

Direct access will be granted to authorised representatives from the Sponsor, host institution

and the regulatory authorities to permit study-related monitoring audits and inspections.

14.2 Protection of Personally Identifiable Information

The participants enrolled into this study will only be identified by a study specific participants

number and/or code in any database. The name or any other identifying details of the

participant will NOT be included in any study data electronic file. The privacy of each

subject and confidentiality of his/her information will be preserved in reports and when

publishing any data. Confidentiality of data will be observed by all parties involved at all

times throughout the clinical study. All data will be secured against unauthorized access. The

study will comply with the General Data Protection Regulations.

14.3 Document and Data Control

14.3.1 Traceability of Documents and Data

The Investigator will ensure accuracy, completeness, legibility and timeliness of the

data reported to the Sponsor on the CRFs and in all required reports.

14.3.2 Recording Data

The CRF will be reviewed by the authorised site personnel. The data reported on the

CRFs shall be derived from source documents and be consistent with these source

documents, and any discrepancies shall be explained in writing or added as comments

via the CRF. Any change or correction to data reported on a CRF shall be dated,

initialed and explained if necessary, and shall not obscure the original entry (i.e. an

Clinical Investigation Plan CRE 027 Date 14 04 20

audit trail shall be maintained); this applies to both written and electronic changes or corrections.

**15.** MONITORING

It is the responsibility of the Sponsor to ensure the clinical investigation is conducted, recorded and

reported according to the approved CIP, subsequent amendment(s), applicable regulations and

guidance documents.

The Sponsor will arrange for a monitoring visit once the first ten subjects have been enrolled. A

subsequent visit will be scheduled, where ten subjects will be randomly selected and then monitored.

The Principal Investigator or institution will provide direct access to source data during and after the

clinical study for monitoring, audits, EC review and regulatory authority inspections, as required. The

Principal Investigator or institution will obtain permission for direct access to source documents from

the hospital administration and national regulatory authorities before starting the clinical study.

Clinical Investigation Plan CRE 027 Date 14\_04\_20 Version Number 1.0

CONFIDENTIAL

Page 35 of 42

#### **16.** ETHICS

#### 16.1 Declaration of Helsinki

The Investigator will ensure that this study is conducted in accordance with the principles of the Declaration of Helsinki.

#### **16.2 Guidelines for Good Clinical Practice**

The Investigator will ensure that this study is conducted in full conformity with relevant regulations and with the ICH Guidelines for Good Clinical Practice and in accordance with ISO14155.

#### 16.3 Approvals

The protocol will be submitted to an appropriate Research Ethics Committee (REC) and host institution(s) for written approval.

The Investigator will submit and, where necessary, obtain approval from the above parties for all substantial amendments to the original approved documents.

#### **17.** COMPLIANCE

#### 17.1 Clinical Trial Agreement

The Investigator will sign a Clinical Trial Agreement and agrees to be compliant with the agreement. The Investigator will not start enrolling patients or requesting verbal consent from any subject prior to obtaining EC approval and relevant regulatory approval, if applicable, and authorisation from the Sponsor in writing before the clinical investigation. If additional requirements are imposed by the EC or relevant regulatory authority, those requirements will be followed. If any action is taken by an EC or a relevant regulatory authority with respect to the clinical study, that information will be forwarded to the Sponsor.

#### 17.2 Insurance

As the Sponsor, Xiros has taken up general liability insurance in accordance with the requirements of the applicable local laws. Insurance certificates/documentation will be provided to the Investigator upon request.

## **18.** SUSPENSION OR PREMATURE TERMINATION OF THE CLINICAL INVESTIGATION

The Sponsor reserves the right to terminate the clinical study at any stage, with appropriate written notice to the Investigators, ECs and relevant authorities, if required.

A Principal Investigator, EC or regulatory authority may suspend or prematurely terminate participation in a clinical study at the study centres for which they are responsible. The Investigators will follow requirements specified in the Clinical Trial Agreement.

The clinical investigation will be concluded when:

- All centres are closed AND
- The final report has been provided to Investigators or the Sponsor has provided formal documentation of clinical study closure.

#### **19.** PUBLICATION

Publications or presentations of clinical study results may be published in an appropriate journal.

#### **20.** REPORTING RESULTS ON CLINICALTRIALS.GOV

This clinical investigation will be registered on ClinicalTrials.gov. A full report of the pre-specified outcomes, regardless of the results, will be made public through ClinicalTrials.gov website no later than 12 months after the clinical investigation completion. If this clinical investigation is terminated early, the Sponsor will make every effort to hasten the release of the pre-specified outcomes through the ClinicalTrials website.

#### **APPENDIX 1**

PATIENT REPORTED OUTCOMES

#### **IKDC Subjective Knee Evaluation**

SYMPTOMS\*:
\*Grade symptoms at the highest activity level at which you think you could function without significant symptoms, even if you are not actually performing activities at this level.

1.	What is the h  4  3  2  1  0	ighest level Very strer Strenuous Moderate Light activ Unable to	nuous ac activitie activitie rities like	ctivities es like h s like m e walkin	like jump leavy ph oderate g, house	oing or p ysical w physica work or	ivoting a ork, skii I work, r gardeni	as in gying or te running ing	mnastice nnis or joggir	s or foot	ball	
2.	During the pa	ast 4 weeks,	or since	e your ir	njury, ho	w often	have yo	u had p	ain?			
	NOVOr	1	2	3 •	4 □	5 🗖	6 □	7 •	8	9 🗖	10 □	Constant
3.	If you have p	ain, how sev	vere is it	:?								
		1	2 □	3 •	4 •	5 □	6	7 •	8	9	10 -	Worst pain imaginable
4.	During the part of	Not at all Mildly Moderatel Very Extremely	у	e your ir	njury, ho	w stiff o	swoller	n has yo	our knee	been?		
5.	What is the h	ighest level Very strer Strenuous Moderate Light activ Unable to	nuous ac activitie activitie rities like	ctivities es like h s like m e walkin	like jump leavy ph oderate g, house	oing or p ysical w physica work or	oivoting a ork, skii I work, r gardeni	as in gying or teal	mnastice nnis or joggir	s or footl		
6.	During the pa	ast 4 weeks,	or since	e your ir	njury, ha	s your k	nee lock	ked or c	aught?			
	₀□Y	es ₁□No										
7.	What is the h  4  3  2  1  0	ighest level Very strer Strenuous Moderate Light activ Unable to	nuous ac activitie activitie rities like	ctivities es like h s like m walkin	like jump leavy ph oderate g, house	oing or p ysical w physica work or	ivoting a ork, skii I work, r gardeni	as in gying or te running or te ing	mnastice nnis or joggir	s or footl	ball	?

#### **SPORT ACTIVITIES**:

8.	What is the	e highe	est level	of activi	ity you c	an parti	icipate in o	n a regula	r basis?			
	4	.□ Ve	ery stren	nuous ac	ctivities I	ike jum	ping or pive	oting as in	gymnastic	cs or foc	otball	
	3	□ St	renuous	activitie	es like h	eavy ph	nysical wor	k, skiing o	r tennis			
	2	Mo	oderate	activitie	s like m	oderate	physical w	ork, runni	ng or jogg	ing		
	1	Lig	ght activ	ities like	e walking	g, house	ework or ga	ardening				
	0	Ur	nable to	perform	any of	the abo	ve activitie	s due to k	nee			
9.	How does	your kı	nee affe	ct your	ability to	:						
						N	ot difficult	Minimal		erately	Extrem	
a.	Go up stai	irs					at all ₄ □	difficul ₃□		ficult	difficu ₁□	lt do ₀□
b.	-						4 -	3 _			1	。 •
C.							4 -	3 _			1□	。 □
d.	What is the highest level of activity you cade   Very strenuous activities like he   Strenuous activities like he   Moderate activities like mode   Light activities like walking   Unable to perform any of the   Unable to perform any of your   Unable to perform any o						4 -	3			1	
e.	•						4 -	3			1	。 □
f.	•					4 3 2			1	° —		
g.	Rise from a chair Run straight ahead Jump and land on your involved leg						4	3			1	₀□
h.	Jump and	rith your knee bent from a chair straight ahead o and land on your involved leg and start quickly				4	3		2		₀□	
i.	Stop and	,			4	3		$_2$		0		
FUNCT	ION·											
												
10.												lent function and (
FUNCT	ION PRIO	R TO Y	OUR KI	NEE IN.	JURY:							
	Couldn't	0	1	2	3	4	5	6 7	8	9	10	No limitation in
perf												daily activities
	activities											,
CURRE	ENT FUNC	TION C	F YOU	R KNEE	: :							
Canno	t perform	0	1	2	3	4	5	6 7	. 8	9	10	No limitation in
							Ď					daily activities

### Lysholm Knee Questionnaire / Tegner Activity Scale

Name:	Date:				
First Last					
Physician:					
- ;					
1. Limp:	5. Pain:				
( a) None	a) None				
○ b) Slight or periodical	Ob) Inconstant and slight during severe exertion				
○ c) Severe and constant	C) Marked during severe exertion				
	$\bigcirc$ d) Marked on or after walking more than 2 km				
2. Support:	e) Marked on or after walking less than 2 km				
( a) None	( f) Constant				
( b) Stick or crutch					
C) Weight-bearing impossible	6. Swelling:				
	( a) None				
3. Locking:	○ b) On severe exertion				
(a) No locking and no catching sensations	C) On ordinary exertion				
( b) Catching sensation but no locking	( d) Constant				
C) Locking occasionally					
Od) Locking frequently	7. Stair-climbing:				
e) Locked joint on examination	a) No problems				
	○ b) Slightly impaired				
4. Instability:	C) One step at a time				
a) Never giving way	( d) Impossible				
Ob) Rarely during athletics or other severe exertion	0.00				
c) Frequently during athletics or other severe exertion (or incapable of participation)	8. Squatting:  (a) No problems				
( d) Occasionally in daily activities	○ b) Slightly impaired				
( e) Often in daily activities	C) Not beyond 90°				
(f) Every step	( d) Impossible				
· · - · · · · · · · · · · · · · · · · ·					

Activity Level Before Injury	Current Activity Level	Activity Level Following Surgery if applicable	
	0	0	Competitive sports Soccer - national and international elite
О	О	C	Competitive sports Soccer, lower divisions Ice hockey Wrestling Gymnastics
0	О	0	Competitive sports Bandy Squash or badminton Athletics (jumping, etc.) Downhill skiing
C	О	0	Competitive sports Tennis Athletics (running) Motorcross, speedway Handball Basketball Recreational sports Soccer Bandy and ice hockey Squash Athletics (jumping) Cross-country track findings both recreational and competitive
0	0	O	Recreational sports Tennis and badminton Handball Basketball Downhill skiing Jogging, at least five times per week
С	О	С	Work Heavy labor (e.g., building, forestry) Competitive sports Cycling Cross-country skiing Recreational sports Jogging on uneven ground at least twice weekly
0	0	0	Work Moderately heavy labor (e.g., truck driving, heavy domestic work) Recreational sports Cycling Cross-country skiing Jogging on even ground at least twice weekly
O	С	С	Work Light labor (e.g., nursing) Competitive and recreational sports Swimming Walking in forest possible
0	0	0	Work Light labor Walking on uneven ground possible but impossible to walk in forest
О	0	0	Work Sedentary work Walking on even ground possible
0	0	0	Sick leave or disability pension because of knee problems

	C	0	О	Work Sedentary work Walking on even ground possible
	0	0	0	Sick leave or disability pension because of knee problems
Гед	gner:			Lysholm Score: Print Form Submit

# 2 Abbreviations and Definitions

ACL	Anterior Cruciate Ligament	
ADE	Adverse Device Effect	
AE	Adverse Event	
IKDC International Knee Documentation Committee		
PROM	Patient Reported Outcome Measure	
SAE	Serious Adverse Event	
SAP	Statistical Analysis Plan	

# 3 Introduction

The ACL is the most commonly injured ligament in the knee. There are many treatment pathways for ACL injury. One approach is reconstruction surgery in which the ruptured ACL is replaced with a biological tendon graft fixed into bone tunnels in the femur and tibia. There are several sources of tendon graft: an autograft from the patient or an allograft from a donor.

The JewelACL is another method for ACL reconstruction. It is a polyester scaffold and is matched in tensile strength to the semitendinosus hamstring tendon. It can be used with or without an additional tissue graft in either partial or total tissue sparing ACL reconstruction procedures. The multicentre study will evaluate patients who received JewelACL for their reconstruction. All patients were followed up for at least 5 years follow up post-surgery. The study will focus on the clinical outcomes of the patient group.

# 4 Study Objectives and Endpoints

## 4.1 Study Objectives

The study will assess the following research questions:

Primary objective:

• To assess at least 5-year re-rupture rate from subjects who were implanted with the JewelACL device for ACL reconstruction.

Secondary objectives:

- To report on all recorded adverse events
- To assess whether fixation type and autograft use have an effect on failure rates
- To assess patient reported outcomes at 5 years minimum (PROMS: IKDC, Lysholm, Tegner)
- To assess changes in patient reported outcome scores from baseline, if available (PROMS: IKDC, Lysholm, Tegner)

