## 4.2 Endpoints

#### 4.2.1 Primary outcome measure

The primary study endpoint is the occurrence of a re-rupture.

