#### 5.3.2 Demographic and Baseline measurements

At the baseline timepoint, or time of the procedure, the following demographic and baseline characteristics of the study participants will be collected:

- Age
- Gender
- Medical History, including history of the knee(s) e.g. previous surgeries
- Participation in sports
- ACL failure injury mode
- Patient reported outcome scores

Additionally, information on the procedure will be collected:

- Hybrid (with autograft) or non-hybrid
- Fixation type (tibial and femoral)
- Other procedures during surgery (e.g. multi-ligament repair, meniscus repair)

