## 7.3 Subgroups

In addition to an analysis of all patients combined, analyses for all outcomes (primary, secondary, safety) will be performed for the following subgroups:

- Patients receiving JewelACL alone
- Patients receiving JewelACL in combination with autograft

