## 8.2 Demographic and Baseline Variables

A summary of patient demographics and baseline measurements are outlined in Section 5.3.2. Descriptive statistics will be produced for these variables, along with baseline values of the secondary outcomes. Summaries will be produced for each site separately, and for all patients combined. The summary statistics will be produced in accordance with section 8.1.

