# 9 Efficacy Analyses

## 9.1 Primary Efficacy Analysis

The primary endpoint is re-rupture, assessed as a binary outcome (yes/no). The number and percentage of patients experiencing a re-rupture at each timepoint will be reported. Additionally, a corresponding 95% confidence interval will be reported for the percentage of patients with a re-rupture.

The summary statistics for the outcome variable will be produced in accordance with Section 8.1. The primary study analysis will be performed using the Full Analysis Population (see section 7.2).

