# 9.2 Secondary Efficacy Analyses

The secondary outcomes are PROMs, all of which are measured on a continuous scale. Summary statistics for these outcomes at 5-years will be produced in accordance with Section 8.1.

At the time of writing, it is unclear whether it will be possible to obtain data on these outcomes at baseline, or at any other point post-surgery. If any such data is obtained, outcomes at these timepoints will be summarised in an equivalent way to the 5-year values.

If data at baseline is obtained, a comparison of the scores at baseline and 5-years will be made. If the changes in outcomes between timepoints are found to follow a Normal distribution, the paired t-test will be used to compare the change in score over time. The mean change will be reported, along with a corresponding 95% confidence interval. If the changes are not found to be normally distributed, the Wilcoxon matched-pairs test will be preferred for the analysis, whilst the median change and corresponding 95% confidence interval will be reported.

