# 12 Summary of Changes to the Analysis Plan

The changes from version 1.0 to 1.1 of the SAP were mostly cosmetic. However, additional subgroups for the primary outcome were added (separate analyses for each fixation type), as well as the addition of demographic summaries by study site.

Between versions 1.1 and 1.2, there was a removal of the plan to analyse by fixation type, as it was felt that there was insufficient variation in the fixation types used. Additionally, a justification of the figures used in the sample size has been added.

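### The objective on fixation type and autograft use is only partly matched by the analysis: no autograft difference is planned, and the objective was not updated when the fixation analysis was dropped

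*SAP*

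**What the plan says.** **Objective.** SAP 4.1 sets the secondary objective "To assess whether fixation type and autograft use have an effect on failure rates". Protocol 7.2 and the synopsis say the same. Protocol 3 promises to assess the impact of both factors, and protocol 5.4 asks about their influence on outcomes more widely.

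**Autograft.** SAP 7.3 states that "analyses for all outcomes (primary, secondary, safety) will be performed for the following subgroups", and names two: JewelACL alone and JewelACL with autograft. Under SAP 9.1, "a corresponding 95% confidence interval will be reported for the percentage of patients with a re-rupture". Protocol 12 (Description of Statistical Methods) likewise plans the analysis separately in the two subgroups.

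**Fixation.** Fixation type is collected (SAP 5.3.2), and SAP 8.2 says of the variables in that section: "Descriptive statistics will be produced for these variables, along with baseline values of the secondary outcomes". Neither SAP 7.3, SAP 9.1 nor protocol 12 breaks re-rupture down by fixation. SAP 12 explains this by the "removal of the plan to analyse by fixation type, as it was felt that there was insufficient variation in the fixation types used".

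**Comparisons.** The only comparison that the SAP specifies is of patient-reported scores within patients, where "the paired t-test will be used to compare the change in score over time" if the changes are Normal, with a Wilcoxon alternative. Protocol 12 says that no hypothesis tests are planned.

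**The concern.** An objective that asks whether a factor affects failure needs a planned result that relates the factor to failure. For fixation there is none. For autograft there are two separate percentages, and the measure of difference, its direction and its interval method are all unspecified.

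Two things follow. A reader with two intervals side by side will compare them by eye, and judging by overlap can mislead. And if the report does give a difference, its form will have been chosen after the data were seen. The objective's effect wording also invites a causal reading that an unadjusted, non-randomised cohort cannot support.

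**Working it through.** **Objective against planned output**

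| Part of the objective | Planned output on failure | Estimate relating the factor to failure |
|---|---|---|
| Autograft use | Number, percentage and 95% CI in each subgroup (SAP 7.3, 9.1; protocol 12) | None planned |
| Fixation type | None; frequencies only (SAP 5.3.2, 8.2) | None planned; removal explained in SAP 12 |

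**The plan's own figure.** Inputs from SAP 6 and protocol 12: p = 0.10, precision d = 0.06, 95% confidence, 20% drop-out.

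- n = 1.96² × 0.10 × 0.90 / 0.06² = 96.04, which reproduces the stated 96.
- 96 / 0.80 = 120, as stated.
- Half-width at 96: 1.96 × √(0.09/96) = 6.0 points.

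That ±6 points applies to the overall rate only.

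**Precision of an autograft difference.** Inputs: 96 evaluable (SAP 6) and the same true rate in both groups, either 10% or 5% because the plan expects 10% or less. The documents give no autograft split, so three are assumed.

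Newcombe interval for d = p1 − p2, from the Wilson limits (l, u) of each group:

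- Wilson limits: [p + z²/2n ± z√(p(1−p)/n + z²/4n²)] / (1 + z²/n), with z = 1.96
- lower limit: d − √[(p1 − l1)² + (u2 − p2)²]
- upper limit: d + √[(u1 − p1)² + (p2 − l2)²]

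Example by hand, 5/48 in each group: p = 10.42% and the Wilson limits are 4.53% and 22.17%. The half-width is √(5.89² + 11.75²) = 13.1, so the difference is 0.0 with a 95% CI of −13.1 to 13.1 points.

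Averaging the half-width over all binomial outcomes, in percentage points:

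| Assumed split | Mean Newcombe, 10% in both | Mean Newcombe, 5% in both | Wald check, 10% in both |
|---|---|---|---|
| 48/48 | 12.8 | 10.6 | 12.0 |
| 24/72 | 14.8 | 12.6 | 13.9 |
| 10/86 | 21.0 | 18.9 | 19.6 |

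The Wald check is 1.96 × √(0.09/n1 + 0.09/n2).

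Two further examples, smaller group minus larger:

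- 2/24 v 7/72: difference −1.4 (95% CI −12.2 to 16.8)
- 1/10 v 9/86: difference −0.5 (95% CI −12.1 to 30.3)

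Nothing can be computed for fixation, because the documents give no distribution of fixation types.

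**The case against.** **The fixation change is disclosed.** SAP 12 records the removal and the reason, and fixation types are still described. This stands. A reader might infer that the analysis was dropped silently or because of the failure results. The documents do not support that: the stated reason concerns how much the fixation types varied, not failures. What remains is an objective line that was not updated. Protocol 12 does require deviations from the original analysis plan to be justified in the final report. But here, following the current plan exactly still leaves the fixation part without a result, so that clause may not catch it.

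**The autograft question is not ignored.** Both subgroup rates are planned with intervals, the point difference is a subtraction, and a reader could build an interval from the counts. This also stands. A reader might infer that the plan cannot answer the autograft part at all; that goes too far. What is missing is one derived interval, with its form fixed in advance.

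**No tests are planned.** True, but a difference with a confidence interval is estimation and needs no test.

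**The interval will say little.** It will be wider than the expected rate and unadjusted. That is a reason to label it exploratory and to soften how the objective is read. It does not justify leaving the comparison to the eye.

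**Asking whether there is an effect does not claim causation.** Fair. A note that the result is a descriptive association is enough.

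**A broad rewrite of the objective would do harm.** This stands and limits the fix. SAP 4.2.1 says "The primary study endpoint is the occurrence of a re-rupture", whereas protocol 7.3 names reconstruction failure, and protocol 9.4.3 to 9.4.5 collect any graft failure. Putting re-rupture into the protocol objective would narrow it without reconciling the two terms. Restricting protocol 5.4 to re-rupture would cut wider wording that SAP 7.3 supports, since patient-reported and safety outcomes are also analysed by autograft group. Deleting the fixation objective would make the change less visible.

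**Conclusion.** The point holds, and it is minor. The autograft part of the objective is partly addressed: two rates with intervals, but no planned difference. The fixation part has no analysis against failure, for a reason that the SAP states openly, under an objective that was never aligned with that decision.

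An added autograft difference would be descriptive. With 96 evaluable patients the mean 95% half-width is about 13 to 21 points at 10% re-rupture in both groups, and about 11 to 19 points at 5%. These figures rest on assumed splits from 48/48 to 10/86 and on equal true rates.

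A reader might also infer that the study is too small. The documents do not support that: the sample size was set for the overall rate and reproduces for that purpose. The primary estimate is likewise untouched.

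**What to change.** 1. **SAP 9.1, add:** *The difference in the percentage with re-rupture (JewelACL with autograft minus JewelACL alone) will be reported with a 95% CI (Newcombe), as an exploratory, unadjusted, non-randomised comparison; no hypothesis test.*
2. **SAP 4.1, keep the objective visible and annotate it:** *The fixation part is not analysed against failure because fixation types varied too little (see section 12); fixation types are described only. The autograft part is a descriptive association.*
3. **Final report:** state that the fixation part of the objective was not answered, and why.
4. **Protocol (synopsis, 3, 5.4, 7.2):** align the wording at the next amendment. Do not delete the objective, replace failure with re-rupture, or narrow outcomes in 5.4.

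**Cost.** A short SAP revision and one interval from counts already planned, with no new data or patients. Protocol 16.3 requires substantial amendments to be submitted and, where necessary, approved. The documents do not say whether this wording change would count as substantial, so it is best carried with the next amendment. The downside is that the reported difference will be imprecise and open to confounding, and must be labelled so.
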